Within 24 hours of admission to the inpatient floor, study subjects will be approached by a member of the research team, and asked for informed consent. Patients that consent to participate and meet our inclusion criteria will be ordered the appropriate study drug by the floor pharmacist, per the Yale Investigative Drug Service's randomization to either the treatment or the placebo arm. Each subject will be ordered a capsule containing either placebo (cellulose microcrystalline) or 5 mg melatonin each evening at 9 p.m. The study drug can be given as early as 7pm on the day of admission, if necessary, to allow treatment to begin within 24 hours of admission to the floor.. The capsules will be prepared and administered by the Yale-New haven Hospital Investigational Drug Service. The capsules will be administered nightly until discharge or a maximum of 2 weeks if the hospitalization is prolonged. The capsule must be swallowed whole and not opened.

Subjects will be assessed twice daily, once in the- a.m. and again in the p.m by the floor nurses for evidence of delirium using the Short CAM (Confusion Assessment Method), which is a validated clinical tool for identifying delirium, and the current standard of practice tool for the diagnosis of delirium. This evaluation should take maximally 5 to 10 minutes to complete.

While it is considered standard of care for nurses to administer the Short CAM once daily at Yale-New Haven Hospital, the twice daily Short CAM is standard of care at the University of Connecticut Hospital but not currently at the Yale-New Haven Health System with the exception of Verdi 4 West where the CAM is administered twice a day for all patients.

The primary endpoint will be the occurrence of delirium as defined by the Short CAM by the time of discharge or prior to hospital day 15, whichever occurs first. The study drug will be continued until the primary end point of delirium is reached, discharge or hospital day 15.

The maximum period of study drug administration will be 14 days. If the patient's length of stay exceeds 14 days the patient's participation in the study will end and the subject will be recorded as having completed the study without delirium. If the primary end point of delirium is reached, the subject will have completed the study, participation will be over and the study drug will no longer be administered.

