While causes of delirium will be extracted from the chart, all investigations will be done by the primary inpatient team. The diagnosis of delirium will be communicated to the inpatient team.

Patients that agree to participate in the study will not be prescribed melatonin as a sleeping aid. All care, including medications for sleep and management of delirium will be per standard of care, as decided by the attending physician of record. If the primary team believes that melatonin is medically indicated the patient will not be enrolled or be withdrawn from the study.

4. Genetic Testing N/A

A. Describe

- i. the types of future research to be conducted using the materials, specifying if immortalization of cell lines, whole exome or genome sequencing, genome wide association studies, or animal studies are planned
- ii. the plan for the collection of material or the conditions under which material will be received
- iii. the types of information about the donor/individual contributors that will be entered into a database
- iv. the methods to uphold confidentiality

B. What are the conditions or procedures for sharing of materials and/or distributing for future research projects?

C. Is widespread sharing of materials planned?

D. When and under what conditions will materials be stripped of all identifiers?

E. Can donor-subjects withdraw their materials at any time, and/or withdraw the identifiers that connect them to their materials?

- i. How will requests to withdraw materials be handled (e.g., material no longer identified: that is, anonymized) or material destroyed)?

F. Describe the provisions for protection of participant privacy

G. Describe the methods for the security of storage and sharing of materials

5. Subject Population: Provide a detailed description of the types of human subjects who will be recruited into this study.

The study will recruit subjects \geq age 65, who are admitted to the four participating general internal medicine floors at St. Raphael's hospital.

6. Subject classification: Check off all classifications of subjects that will be specifically recruited for enrollment in the research project. Will subjects who may require additional safeguards or other considerations be enrolled in the study? If so, identify the population of subjects requiring special safeguards and provide a justification for their involvement.

- | | | |
|---|--|--|

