|  Children |  Healthy |  Fetal material, placenta, or dead fetus |
|  Non-English Speaking |  Prisoners |  Economically disadvantaged persons |
|  Decisionally Impaired |  Employees |  Pregnant women and/or fetuses |
|  Yale Students |  Females of childbearing potential | |

If patients are not competent to sign the informed consent, we will contact the healthcare proxy to provide informed consent for enrollment.

NOTE: Is this research proposal designed to enroll children who are wards of the state as potential subjects? Yes No (If yes, see Instructions section VII #4 for further requirements)

7. **Inclusion/Exclusion Criteria:** What are the criteria used to determine subject inclusion or exclusion?

Inclusion Criteria

- Age \geq 65
- Inpatient admission to general internal medicine service

Exclusion Criteria

- Expected lifespan or length of stay \leq 48 hours
- Non-English speaking
- Already taking melatonin at the time of randomization (at least one dose taken in the prior week)
- Already taking ramelteon (Rozerem) at the time of randomization (at least one dose taken in the prior week)
- Presence of delirium at the time of randomization
- Unable to take oral medications
- Subject or proxy unable to provide informed consent
- Unable to give consent within 18 hours of invitation or within 24 hours of being admitted to the medical floor
- Known allergy to melatonin
- Patients taking warfarin, nifedipine and fluvoxamine
- Patients with severe liver impairment (admission diagnosis of active liver disease such as cirrhosis or acute hepatitis)
- Unable to recall at least 2 of 3 words after distraction by asking the subject to name the days of the week backwards starting with Sunday.

8. How will **eligibility** be determined, and by whom?

A member of the research team will use the hospital EMR to screen admissions to the four participating general Internal Medicine floors for eligibility, based on the above inclusion and exclusion criteria. This will be accomplished via the OnCore and YCCI EPIC Support Services. The consent process will include a brief description of the study with an

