The principal investigator is responsible for monitoring the data, assuring protocol compliance, and conducting the safety reviews at the specified frequency on a monthly basis. During the review process the principal investigator will evaluate whether the study should continue unchanged, require modification/amendment, or close to enrollment.

The principal investigator or the Institutional Review Board (IRB) have the authority to stop or suspend the study or require modifications.

This protocol presents minimal risks to the subjects and adverse events or other problems are not anticipated. In the unlikely event that such events occur, Reportable Adverse Events (which are events that are serious or life-threatening and unanticipated (or anticipated but occurring with a greater frequency than expected) and possibly, probably, or definitely related) or unanticipated problems involving risks to subjects or others will be reported in writing within 48 hours to

the IRB (using the appropriate forms from the website) and any appropriate funding and regulatory agencies. The investigator will apprise fellow investigators and study personnel of all adverse events that occur during the conduct of this research project through regular study meetings.

- d. For multi-site studies for which the Yale PI serves as the lead investigator:
- i. How will adverse events and unanticipated problems involving risks to subjects or others be reported, reviewed and managed?
 - ii. What provisions are in place for management of interim results?
 - iii. What will the multi-site process be for protocol modifications?

12. **Statistical Considerations:** Describe the statistical analyses that support the study design.
13.

Primary Outcome:

Incidence of delirium per admission of medical geriatric patients

Incidence of delirium per patient days of hospitalization in medical admission of geriatric patients

Secondary outcomes:

Risk factors associated with incident delirium

Duration of delirium by study group

Hospital length of stay

Sample size based was estimated using openepi.com (similar results with Stata version 14 sample size calculator) based on control group incidence of delirium in medical subgroup of 30%. (Chen et al: Exogenous melatonin for delirium prevention: a meta-analysis of randomized controlled trials - Molecular Neurobiology online publication 21 July 2015) with relative risk reduction of 30 %.

Sample Size: X-Sectional, Cohort, & Randomized Clinical Trials

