Two-sided significance level(1-alpha):	95
Power(1-beta, % chance of detecting):	80
Ratio of sample size, Unexposed/Exposed:	1
Percent of Unexposed with Outcome:	30
Percent of Exposed with Outcome:	21
Risk/Prevalence Ratio:	0.7
Risk/Prevalence difference:	-9

Sample size estimation by the Fleiss method yielded a total sample size of 734 with 367 in each group.

Descriptive statistics such as percentages for binary categorical variables, means and standard deviations for continuous variables. Fisher's exact test or chi-square test will be used to compare categorical variables. For continuous variables we will use t-test of unequal variances for means for normally distributed variables and the Wilcoxon-Mann-Whitney where normal distribution cannot be assumed. Risk ratio will be calculated using Stata statistical program version 14. (StataCorp LP, [name]) Associations with covariates will be tested using logistic regression with presence of incident delirium as the dependent variable.

Person days to delirium will be compared between the two groups using Survival analysis with Kaplan Meier curves, logrank test and Cox proportional hazards (covariates include age, comorbidities, medication numbers, presence of risk factors for delirium – polypharmacy, use of psychotropic or sedating medications, and use of bladder catheters).

Upon completing enrollment and analysis of 367 subjects, [name], a independent statistical expert, will analyze the data. In addition, an independent geriatrician expert in delirium will review any equivocal CAM results and make a decision as to the occurrence of delirium.

SECTION VI: RESEARCH INVOLVING DRUGS, BIOLOGICS, RADIOTRACERS, PLACEBOS AND DEVICES

If this section (or one of its parts, A or B) is not applicable, state N/A and delete the rest of the section.

A. DRUGS, BIOLOGICS and RADIOTRACERS

1. **Identification of Drug, Biologic or Radiotracer:** What is (are) the **name(s)** of the drug(s) biologic(s) or radiotracer(s) being used? Identify whether FDA approval has been granted and for what indication(s).

Melatonin—FDA categorized as a dietary supplement for sleep aid

All protocols which utilize a drug, biologic or radiotracer **not** approved by, but regulated by, the FDA, or a radiotracer regulated by the RDRC, must provide the following information:

a. What is the Investigational New Drug (IND) **number** assigned by the FDA?

FDA IND 129224-Melatonin

b. Who holds the IND?

[name]

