Note: If the YNHH IDS (or comparable service at CMHC or WHVA) will not be utilized, explain in detail how the PI will oversee these aspects of drug accountability, storage, and preparation.

4. **Use of Placebo:** **Not applicable to this research project**

If use of a placebo is planned, provide a justification which addresses the following:

a. Describe the safety and efficacy of other available therapies. If there are no other available therapies, state this.

There are currently no approved therapies for the prevention of delirium.

²⁹ Andersen, L. P., Gogenur, I., Rosenberg, J., & Reiter, R. J. (2015). The Safety of Melatonin in Humans. *Clin Drug Investig.* doi: 10.1007/s40261-015-0368-5

- b. State the maximum total length of time a participant may receive placebo while on the study.

2 weeks

- c. Address the greatest potential harm that may come to a participant as a result of receiving placebo.

There is no potential harm associated with use of placebo except as noted in section 9. The placebo will be prepared by the Yale Investigational Drug Service and will consist of cellulose microcrystalline in a capsule

- d. Describe the procedures that are in place to safeguard participants receiving placebo.

Each patient will be observed in the hospital by the research team and any complications will be noted. If the patient cannot swallow without compromise then they will be removed from the trial.

6. Use of Controlled Substances:

Will this research project involve the use of controlled substances in human subjects?

Yes No *See HIC Application Instructions to view controlled substance listings.*

If yes, is the use of the controlled substance considered:

Therapeutic: The use of the controlled substance, within the context of the research, has the potential to benefit the research participant.

Non-Therapeutic: *Note, the use of a controlled substance in a non-therapeutic research study involving human subjects may require that the investigator obtain a Laboratory Research License. Examples include controlled substances used for basic imaging, observation or biochemical studies or other non-therapeutic purposes. See Instructions for further information.*

7. Continuation of Drug Therapy After Study Closure **Not applicable to this project**

Are subjects provided the opportunity to continue to receive the study drug(s) after the study has ended?

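### Kaplan-Meier curves are planned for in-hospital delirium with no rule for discharge or death; if discharge is censored, they overstate in-hospital risk in each arm

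*Combined protocol and SAP*

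**What the plan says.** Section V.12 (Statistical Considerations) plans the time-to-event analysis: "Person days to delirium will be compared between the two groups using Survival analysis with Kaplan Meier curves, logrank test and Cox proportional hazards".

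Section V.3 (Research Plan) limits when the endpoint can occur: delirium counts "by the time of discharge or prior to hospital day 15, whichever occurs first". It gives two rules for the end of observation:
- After delirium: "If the primary end point of delirium is reached, the subject will have completed the study, participation will be over".
- For a stay longer than 14 days: "the subject will be recorded as having completed the study without delirium".

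Withdrawal is also possible, for example under Section V.3: "If the primary team believes that melatonin is medically indicated the patient will not be enrolled or be withdrawn from the study".

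No section says how the survival analysis treats a subject who is discharged or dies without delirium. Mortality appears only among the data items in Section VIII. Hospital length of stay is a secondary outcome in Section V.12, but no mean or distribution is given.

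**The concern.** Once a subject goes home or dies, in-hospital delirium can no longer occur. At the planned rates about 70% of control and 79% of melatonin subjects never have the event, and apart from deaths, withdrawals and stays past the window they leave by discharge. The competing event is therefore the usual outcome.

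Kaplan-Meier with discharge censored estimates the risk that would apply if nobody left. That is a different quantity from the per-admission incidence, which is one of the trial's own primary outcomes. The two would appear side by side and could disagree visibly. A reader who takes absolute risk, or the difference between arms, from the curves would be misled.

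**Working it through.** **The plan's own figure.** Fleiss formula without continuity correction, 30% vs 21%, two-sided 5%, 80% power, mean proportion 0.255:

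n = [1.960·√(2·0.255·0.745) + 0.842·√(0.30·0.70 + 0.21·0.79)]² / 0.09² = (1.2081 + 0.5160)² / 0.0081 = 366.99, so 367 per arm and 734 in total. This matches Section V.12. It is based on proportions per admission and does not depend on the curves.

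**Inputs.** From Section V.12: in-hospital incidence 30% vs 21% (gap 9 points, ratio 0.70). From Section V.3: observation ends at discharge or before hospital day 15. Assumed, because the documents do not give them: mean stay without delirium of 5 or 7 days, alike in both arms and independent of delirium risk; constant delirium hazard λ over the first W days and zero afterwards. Section V.7 excludes patients whose "Expected lifespan or length of stay" is 48 hours or less, but actual stays may be shorter than expected. Stays are therefore modelled both with a two-day minimum and with none.

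**Formulas.** With S(t) the probability of still being in hospital, ignoring delirium:
- In-hospital incidence = ∫₀ᵂ λ·exp(−λt)·S(t) dt. Solve for λ so that this equals 0.30 or 0.21.
- Curve with discharge censored: 1-KM at day 14 = 1 − exp(−λW).

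**One case by hand.** Exponential stay, no minimum, mean 5 days (discharge rate μ = 0.2), W = 7. The integral is λ/(λ+μ)·[1 − exp(−(λ+μ)W)].
- Control, λ = 0.1034: 0.3408 × 0.8804 = 0.300; 1-KM = 1 − exp(−0.724) = 0.515.
- Melatonin, λ = 0.0662: 0.2487 × 0.8449 = 0.210; 1-KM = 1 − exp(−0.463) = 0.371.

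**All equal-stay cases: 1-KM, control/melatonin, %.** The in-hospital incidence is 30/21 in every cell.

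| Stay model | Mean | W=3 | W=5 | W=7 | W=14 |
|---|---|---|---|---|---|
| 2-day minimum + gamma (shape 3) | 5 | 30.2/21.1 | 33.9/23.9 | 40.8/29.2 | 63.9/48.8 |
| | 7 | 30.1/21.0 | 31.4/22.1 | 34.8/24.6 | 52.2/38.4 |
| 2-day minimum + exponential | 5 | 31.3/22.0 | 37.1/26.3 | 44.0/31.6 | 65.6/50.0 |
| | 7 | 30.8/21.6 | 34.5/24.3 | 39.0/27.7 | 55.5/40.8 |
| No minimum, gamma (shape 3) | 5 | 32.6/22.9 | 37.5/26.5 | 43.8/31.3 | 65.4/49.8 |
| | 7 | 31.2/21.9 | 33.8/23.8 | 37.5/26.5 | 53.7/39.4 |
| No minimum, exponential | 5 | 38.9/27.5 | 45.2/32.2 | 51.5/37.1 | 70.8/53.8 |
| | 7 | 36.3/25.6 | 40.7/28.8 | 45.2/32.2 | 60.5/44.4 |

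- W = 3 to 7: gap 9.0 to 14.4 points, ratio 0.70 to 0.72.
- W = 14 (constant hazard throughout): gap 13.9 to 17.0 points, ratio 0.73 to 0.76.

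A simulation of 200,000 per arm (two-day minimum + gamma, mean 5, W = 7) gave 1-KM of 40.9% vs 29.3%. Aalen-Johansen on the same data gave 30.1% vs 21.0%.

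**Unequal stays.** Two-day minimum, control mean 5 days, incidence still 30% vs 21%:

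| Case | Melatonin mean 4: gap, ratio | Melatonin mean 6: gap, ratio |
|---|---|---|
| Gamma, W=5 | 7.4, 0.78 | 11.2, 0.67 |
| Gamma, W=7 | 6.7, 0.84 | 14.5, 0.64 |
| Exponential, W=7 | 8.5, 0.81 | 14.7, 0.66 |

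The gap can therefore shrink or widen, and the ratio can move either way from 0.70.

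**The case against.** The strongest reply is that the effect is one of presentation only. Section V.12 uses the curves to compare person-days to delirium, which is a rate question, and censoring at discharge is coherent for that. Absolute risk comes from the per-admission incidence and risk ratio, where discharge without delirium is simply a non-event. The documents do not plan to report a day-14 risk from the curves. All of this stands, and it keeps the point minor.

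The bias is also conditional. If discharged subjects were kept event-free to the end of the window, the curves would give 30% vs 21% without distortion. That stands too. But the plan does not say which convention applies, and censoring is the usual default.

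The constant-hazard values are an extreme. At a 5-day mean stay, those models leave only about 0.1 to 6.5 of 367 control subjects at risk at day 14. For exponential stays with no minimum: 367 × exp(−0.0879 × 14) × exp(−0.2 × 14) = 6.5. The trial could barely estimate a curve there, so these figures should not be read as the expected size.

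A reader might infer that the curves always exaggerate the gap between arms and leave the ratio nearly intact. The documents do not support that as a general statement. It requires equal stays, and length of stay is itself an outcome that may differ by arm. Even with equal stays, the ratio drifts toward 1 when onset is not early.

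**Conclusion.** The concern holds as a minor one. The plan names Kaplan-Meier curves for an endpoint that ends at discharge and gives no rule for discharge or death. If discharge is censored, each arm's curve overstates in-hospital risk whenever delirium-free subjects leave before later onsets.

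Under equal mean stays of 5 to 7 days and onset in the first 3 to 7 days, the overstatement runs from none to 51.5% vs 37.1%, against a true 30% vs 21%. These sizes rest on assumed stay and onset distributions. Only the direction within each arm is robust. The direction of the error in the gap and in the ratio depends on whether stays differ by arm.

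A reader might go further and conclude that the main comparison, the sample size or the tests are biased. They are not. The per-admission risk ratio and N=734 use proportions per admission, and logrank and Cox with discharge censored remain valid as cause-specific comparisons.

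**What to change.** In Section V.12, replace the Kaplan-Meier curves with Aalen-Johansen cumulative incidence of delirium by arm to the end of the window (before hospital day 15). Treat discharge alive and death as competing events, and censor only at withdrawal or at the end of the window. Keep logrank and Cox, and label both as cause-specific.

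The cost is a few sentences of analysis-plan wording and a few lines of code. Section VIII already lists admission date, length of stay, mortality and the daily CAM result. The randomisation date should be in the study pharmacy's records (an assumption). The one downside is that the curves no longer correspond directly to the logrank test; the figure legend should say so.

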Another possible risk involves potential breach of confidentiality with the collection of protected patient information. All patients in the study will be initially de-identified by use of medical record number and subsequently further de-identified by receiving a study number. Paper records will be kept in a locked office and computerized records will be kept in a secure hospital computer.

10. **Minimizing Risks:** Describe the manner in which the above-mentioned risks will be minimized.

Regarding the lack of ability to take melatonin for sleep; this risk is minimal, as melatonin is rarely used as a sleeping aid on the participating services. Currently only 7.2% of patients admitted to Celantano 3 and 12.3% of patients admitted to V4 West receive melatonin for

sleep. Clinicians will continue to treat insomnia with the usual non-pharmacologic and pharmacologic methods.

All patient data will be logged in a password protected YCCI / OnCore grid that will only be accessed by study personnel. All participants in the study will be HIPAA and HSPT trained.

The investigation team will review all patients, in EPIC or in person twice per day. Any possible complications will be followed closely.

11. **Data and Safety Monitoring Plan:** Include an appropriate Data and Safety Monitoring Plan (DSMP) based on the investigator's risk assessment stated below. (Note: the HIC will make the final determination of the risk to subjects.) For more information, see the Instructions, page 24.

- a. What is the investigator's assessment of the overall risk level for subjects participating in this study?

There is minimal risk anticipated for subjects participating in this study. Melatonin is considered a safe, over-the-counter, non-prescription supplement. A recent review²⁹ concluded that "Melatonin is safe for short-term use, even when given in extreme doses. Mild adverse effects, such as dizziness, headache, nausea and sleepiness have been reported in levels corresponding to placebo treatments." Section 9 lists Micromedex's side effect profile.

- b. If children are involved, what is the investigator's assessment of the overall risk level for the children participating in this study?

Not applicable

- c. Include an appropriate Data and Safety Monitoring Plan. Examples of DSMPs are available here <http://www.yale.edu/hrpp/forms-templates/biomedical.html> for

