Yes If yes, describe the conditions under which continued access to study drug(s) may apply as well as conditions for termination of such access.

No If no, explain why this is acceptable.

SECTION VII: RECRUITMENT/CONSENT AND ASSENT PROCEDURES

1. Targeted Enrollment: Give the number of subjects:

- a. targeted for enrollment at Yale for this protocol: 734
(367 patients in the treatment and 367 patients in the placebo group)

2. Indicate recruitment methods below. Attach copies of any recruitment materials that will be used.

Flyers

Internet/Web Postings

Radio

- | | | |
|---|---|-------------------------------------|
|  Posters |  Mass E-mail Solicitation |  Telephone |
|  Letter |  Departmental/Center Website |  Television |
|  Medical Record Review |  Departmental/Center Research Boards |  Newspaper |
|  Departmental/Center Newsletters |  Web-Based Clinical Trial Registries | |
|  YCCI Recruitment database |  Clinicaltrials.gov Registry (do not send materials to HIC) | |
|  Other (describe): subjects that meet inclusion criteria will be approached by a member of the research team upon admission to the hospital and recruited for the study. | | |

3. Recruitment Procedures:

- a. Describe how potential subjects will be identified.

Utilizing OnCore and it's EPIC Support Team, a member of the research team will screen the list of admitted patients to the participating services daily to identify all new admissions who are appropriate candidates to enter the study. The electronic chart will then be reviewed to determine if the potential subjects meet all eligibility criteria and if concern for discharge within 48 hours is an issue then the primary treating team will be approached for their prediction/plan.

- b. Describe how potential subjects are contacted.

They will be approached on the medicine floor to which they are admitted by a member of the research team Within 24 hours of admission.

- c. Who is recruiting potential subjects?

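### The between-arm Cox model adjusts for sedating-drug and catheter use without saying when these are measured; if the in-stay fields listed for collection are used, it can remove part of melatonin's effect

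*Combined protocol and SAP*

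**What the plan says.** Section V.12 (Statistical Considerations) compares person-days to delirium between the two groups by Kaplan-Meier curves, a logrank test and a Cox model. The Cox covariates are age, comorbidities, number of medications and a set of delirium risk factors: polypharmacy, "use of psychotropic or sedating medications, and use of bladder catheters". Neither V.12 nor any other section says whether these are baseline values, whole-stay values or time-varying. Associations with covariates are given a separate logistic regression, so the Cox model is a comparison of the arms and not the risk-factor analysis.

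Section VIII.a lists the data to be collected. The items that match the two covariates are as-needed sleep medication, the number of as-needed antipsychotic doses and placement of a Foley catheter. No admission or home medication item is listed.

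On sleep treatment, Section VI.A.1 describes melatonin as "categorized as a dietary supplement for sleep aid". Section V.3 says "Patients that agree to participate in the study will not be prescribed melatonin as a sleeping aid", and that "All care, including medications for sleep and management of delirium will be per standard of care". Section V.10 adds: "Clinicians will continue to treat insomnia with the usual non-pharmacologic and pharmacologic methods".

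**The concern.** A randomised comparison may be adjusted for anything fixed before randomisation. Adjusting for something that treatment can change is different: the adjusted HR then leaves out whatever part of the effect passes through that variable.

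The documents supply both links of such a path for sleep drugs. The study drug is a sleep aid and other drug treatment of insomnia continues, so patients on placebo could need more of it. V.12 itself classes sedating drugs as a risk factor for delirium. An analyst who fits the planned model with the fields listed in VIII.a would be entering in-stay values.

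At stake is the adjusted HR. It appears to serve the second listed primary outcome, incidence per patient days, although the plan does not state that link. It could differ from the unadjusted result for a reason that has nothing to do with baseline imbalance.

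**Working it through.** **Planned effect.** V.12 gives 30% on control, 21% on melatonin, two-sided 5%, 80% power and 367 per arm. The Fleiss formula without continuity correction reproduces the sample size:

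n = [1.96·√(2·0.255·0.745) + 0.842·√(0.30·0.70 + 0.21·0.79)]² / 0.09² = 367 per arm, 734 in total.

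The concern changes nothing in this figure.

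**Implied HR.** Assuming proportional hazards and complete 14-day follow-up, HR = ln(0.79)/ln(0.70) = 0.661. Expected events are 367 × 0.30 = 110.1 and 367 × 0.21 = 77.07. SE(log HR) = √(1/110.1 + 1/77.07) = 0.1485, so the approximate 95% CI is 0.49 to 0.88.

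**Assumed inputs.** The only sleep-drug rates in the documents are in V.10: "Currently only 7.2% of patients admitted to Celantano 3 and 12.3% of patients admitted to V4 West receive melatonin for" sleep. I used 7.2 and 12.3 points as the arm difference in sedating-drug use. That supposes every such placebo patient gets a sedating drug instead and no such melatonin patient does. Use on placebo (p0 = 20%) and the hazard multiplier for sedating drugs (h = 1.5 or 2) are my assumptions.

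**Method.** Keep the arm risks at 30% and 21%.

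1. Solve (1 − p0)·e^(−H) + p0·e^(−Hh) = 0.70 for the 14-day cumulative hazard H of a placebo non-user.
2. Solve (1 − p1)·e^(−Hb) + p1·e^(−Hbh) = 0.79 for b, the adjusted HR.
3. Share of the log HR removed = 1 − ln(b)/ln(0.661).

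Example with p1 = 0.077 and h = 2: step 1 gives H = 0.303; step 2 gives b = 0.727; the share removed is 23%.

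| Use, placebo vs melatonin | h | Adjusted HR | Log HR removed | Shift in SE |
|---|---|---|---|---|
| 20% vs 20% | 2 | 0.657 | −1.5% | below 0.1 |
| 20% vs 12.8% | 1 | 0.661 | 0% | 0 |
| 20% vs 12.8% | 1.5 | 0.681 | 7.3% | 0.20 |
| 20% vs 12.8% | 2 | 0.697 | 12.7% | 0.35 |
| 20% vs 7.7% | 1.5 | 0.697 | 13.0% | 0.36 |
| 20% vs 7.7% | 2 | 0.727 | 23.1% | 0.65 |

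With p0 between 15% and 40%, the last row runs from 0.730 to 0.719. A simulated Cox fit in 800,000 patients gave 0.682, 0.694 and 0.726 for rows 3, 4 and 6.

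**A second way of counting.** V.3 ends participation at delirium, so exposure might be counted only until onset and entered as yes/no. In simulation with equal use in both arms, no effect of use on delirium, complete 14-day follow-up and assumed daily start rates of 0.02 to 0.20, the arm HR was 0.664 to 0.683, against 0.66 unadjusted. This effect on the arm comparison is small, and it would apply equally to catheters.

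**The case against.** The strongest reply is that V.12 means baseline values. The items stand beside age and comorbidities as risk factors, which reads naturally as patient characteristics. VIII.a answers a privacy question and is not a data dictionary: it also lacks a medication count and polypharmacy, both of which are Cox covariates. Its as-needed fields could be meant for the separate risk-factor analysis. This stands as far as it goes: the plan is open to the faulty analysis but is not shown to intend it. It does not settle the matter, because the only listed data that fit these covariates are in-stay.

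The second reply concerns size. The V.10 rates come from two of the four units and from all admissions. V.3 says patients for whom the team judges melatonin medically indicated are not enrolled or are withdrawn, and V.7 excludes anyone who took melatonin in the prior week. Withholding non-study melatonin also applies to both arms and by itself creates no difference. All of this stands, so the 7.2 and 12.3 point differences are likely too large. Even the worst row, with the SE held at 0.1485, has a 95% CI of about 0.54 to 0.97. Its expected z is 2.14, which is power of about 57% against about 80% unadjusted. Every modelled mediation shift is toward no effect, so none creates a false benefit.

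A reader might infer that the adjustment could abolish the effect. Simulation does bring the adjusted HR to 0.96, but only with use of 50% against 20% and a threefold hazard, and nothing in the documents supports such figures. A reader might also infer that antipsychotics given for delirium would enter as predictors of it. V.3 ends participation at onset. Duration of delirium is a secondary outcome and needs later data, but nothing says that the drug fields run past onset.

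**Conclusion.** The concern holds in conditional form. V.12 leaves the timing of two covariates open, and use of the listed in-stay fields as fixed covariates would condition the arm comparison on post-randomisation variables. The path that matters is sleep-drug use; the documents give no route from melatonin to catheter use.

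The size cannot be derived from the documents. The shift from 0.66 to between 0.68 and 0.73 rests on assumed use, an assumed hazard multiplier and differences at the upper end of what V.10 could support. If use does not differ by arm, there is no material change, and the documents do not show that it does.

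A reader might conclude that the trial's main result is biased. The documents do not support that: the risk ratio, chi-square or Fisher test, Kaplan-Meier curves, logrank test and sample size do not use these covariates. Whether the adjusted or the unadjusted HR should be named in advance, and how the logistic risk-factor analysis should handle exposure timing, are separate questions that this point does not decide. It should be fixed, because the change is specific and cheap.

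**What to change.** In V.12, state that every covariate in the between-arm Cox model is a value fixed at or before randomisation: age, comorbidities, medication count on admission, psychotropic or sedative use before randomisation, and a catheter in place at randomisation. Section VII.3.a already provides a source: "The electronic chart will then be reviewed to determine if the potential subjects meet all eligibility criteria".

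Report in-stay sleep drugs, antipsychotics and newly placed catheters by arm as description, and do not use them to adjust the arm effect.

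The cost is a few sentences in V.12 and a few extra baseline fields to abstract from a chart that is already open at screening. If baseline values were always intended, the change only records that.
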